# 2.2.4. Development of a lyophilized S95014 formulation

Different formulations containing different quantitative and qualitative compositions of cryoprotectants were investigated to identify the best product composition that could withstand the lyophilization process and guarantee the production of high-quality drug product with improved stability. The lyophilized S95014 powder for Injection is provided in a single-use vial which after reconstituted will contain 3,750 U/5mL of active PEGylated L-asparaginase [750 U/mL after reconstitution with 5.2 mL of sterile water for injection (SWFI)], which is equivalent to the strength of liquid S95014. The lyophilized S95014 formulation has a longer shelf-life as compared to the liquid formulation (36 months vs 8 months).

A comparative, single-dose and 4-week repeat dose, pharmacokinetic and pharmacodynamic preclinical study of IV administered liquid and lyophilized S95014 formulations was performed in dogs. In this study, lyophilized S95014 has been demonstrated to be equivalent to the original liquid S95014.

S95014 liquid formulation had been authorized by centralized review procedures in 28 countries in the European Union (EU) and 3 countries in the European Economic Area (EEA) in first line treatment of ALL in 2016. The lyophilized formulation of S95014 demonstrated pharmacokinetic/pharmacodynamic comparability through comprehensive analytical and non-clinical comparability assessment recommended by the Committee for Medical Products for Human Use (CHMP) of the European Medicines Agency (EMA). Consequently, the use of lyophilized formulation for S95014 was approved by centralized review procedures in 28 countries in the EU and 3 countries in the EEA in 2017.

### 2.2.5. Study rationale and design

This phase II, parallel, open-label single dose pharmacokinetics (PK) study aims to demonstrate the pharmacokinetic comparability of both liquid and lyophilized S95014 formulations in newly-diagnosed paediatric ALL patients.

S95014 will be intravenously administered at the labelled dose of 2500 U/m², during the induction phase, in at least 78 paediatric patients. Patients will receive other backbone chemotherapeutic regimen as per ALL-MB 2015 protocol (see Appendix 1).

Lyophilized S95014 formulation is widely used in many European countries since its approval in 2017. Moreover, the review of the safety information from post-marketing setting globally has not revealed any noticeable differences between the two presentations. For further details about the risks of lyophilized S95014 administration, please refer to the latest version of the Investigator's Brochure.

The study will be conducted in compliance with the protocol, GCP, the ethical principles that have their origin in the Declaration of Helsinki and the applicable regulatory requirements.

### 3. STUDY OBJECTIVES AND ENDPOINTS

# 3.1. Primary objective

To compare the pharmacokinetics (PK) of both lyophilized and liquid S95014 formulations during the induction phase after a single IV dose in newly diagnosed paediatric patients with ALL

# 3.2. Secondary objectives

- To describe the PK of S95014 after administration of either lyophilized or liquid formulation
- To evaluate the occurrence of treatment emergent adverse events (TEAEs) including serious adverse events (SAEs), regardless of causality and severity, based on National Cancer Institute (NCI) Common Terminology Criteria for Adverse Events (CTCAE) 5.0
- To evaluate the achievement of plasma asparaginase activity (PAA) of ≥0.1 U/mL after the administration of either lyophilized or liquid S95014
- To assess the immunogenicity of both lyophilized and liquid S95014 formulations

# 3.3. Exploratory objectives

Not applicable

# 3.4. Endpoints

Table (3.4) 1 - Endpoints

	Objectives	Endpoints				
Primary	To compare the PK of both lyophilized and liquid S95014 formulations during the induction phase after a single IV dose (2500 U/m²) in newly diagnosed paediatric patients with ALL	PK parameters of S95014 in plasma (C max , AUC)				
Secondary	
 
To describe the PK of S95014 after administration of either lyophilized or liquid formulation
 
To evaluate the achievement of PAA of
 
	Additional PK parameters from the ones defined as primary endpoints (e.g. $C_{trough}$ 14 days post-dose, $T_{max}$ , $T_{1/2}$ )				
	
 
≥0.1 U/mL after the administration of either lyophilized or liquid S95014
 
To assess the immunogenicity of both
 
	PAA on Day 10, Day 17, Day 21 and Day 28 of induction (7, 14, 18- and 25-days post dose)				
	lyophilized and liquid S95014 formulations - To evaluate the occurrence of TEAEs	Anti S95014 $\pm$ anti-PEG antibodies at pre-dose, 14 days and 25 days post dose				
	including SAEs, regardless of causality and severity, based on NCI CTCAE 5.0	Safety tolerance profile of S95014 assessed by incidence and severity of AEs and SAEs  - Laboratory tests: haematology with differential, blood biochemistry, coagulation, urinalysis, hepatitis markers and pregnancy test				

Please refer to section 7, 8, and 9 for further details.

### 4. STUDY DESIGN

# 4.1. Investigational plan

# 4.1.1. Study plan

This is a multicentre, national, randomized, open-label, phase II clinical study comparing the pharmacokinetics of lyophilized and liquid Pegaspargase (Oncaspar®, S95014) formulations in the treatment of newly diagnosed, untreated pediatric patients with ALL. Considering the risk of immunogenicity and hypersensitivity with S95014, it was decided to conduct a parallel study.

Written informed consent and assent (when appropriate) will be obtained from each patient and/or his/her parent(s)/legal representative before initiation of study procedures (see section 13.3). Patients will undergo screening after giving informed consent and will be included once all eligibility requirements for the study have been met. Baseline evaluations and risk stratification will be performed in compliance with the current ALL-MB 2015 protocol.

Each patient will be randomly assigned (1:1) to either lyophilized (arm 1) or liquid (arm 2) S95014 intravenously at the dose of 2500 U/m^2 at Day 3, in combination with other backbone chemotherapy agents as per local practice (see Appendix 1).

The study duration will be approximately 1.5 month, including the screening (14 days) and the treatment period consisting of the induction phase (approximately 30 days). After completing the induction phase, patient will be discontinued from the study and, provided that the inclusion/non-inclusion criteria are fulfilled, will be proposed to enter into a roll-over study (CL2-95014-003) for the consolidation phase.

For more details about the statistical analyses and the sample size calculation please refer to the Section 10.

The study plan is shown in Figure (4.1.1) 1.

In case of non-inclusion of a participant, it is the investigator's responsibility to ensure, in accordance with the local standards of care and medical practices that:

- The reason of non-inclusion is explained to the participant,
- Any event associated with any procedure/condition required by the study protocol (e.g. an event occurring following the discontinuation of a forbidden treatment) is collected,
- An adequate alternative medical care is proposed to the participant.

A non-inclusion visit is not mandatorily carried out, provided these requirements are met and documented in the medical file of the participant.

[figure not shown]

Figure (4.1.1) 1 – Study plan

The study will be divided into the following periods for each participant:

- Screening visit (up to 14 days prior to inclusion): to obtain informed consent and check the screening/non-screening criteria.
- Screening period (Day -14 to Day -1): to check the eligibility of the patient to be included and randomized in the study within 14 days prior to the inclusion.
- **Inclusion visit (Day 0)**: to check inclusion/non-inclusion criteria and to confirm inclusion of the patient in the study
- Randomization (Day 3): the day of S95014 infusion (i.e. Day 3), included patients will be randomly assigned to one of the two treatment groups:
  - Lyophilized S95014 (arm 1)
  - Liquid S95014 (arm 2)
- **Treatment period:** treatment period will start from the day of S95014 infusion, corresponding to Day 3 of the induction phase, until the withdrawal/end-of-study visit.
- Withdrawal/End-of-study visit: at least 30 days after S95014 infusion (i.e. Day 33) and before starting the consolidation phase. During the withdrawal/end-of-study visit, patients will be proposed to participate in a roll-over study (CL2-95014-003) for the consolidation phase using lyophilized S95014 in combination with backbone regimen as per ALL-MB 2015 protocol.

The study start is defined as the date of the first visit of the first participant.

End of Trial is defined as the date of the last visit of the last participant.

### 4.1.2. Investigation schedule

Table (4.1.2) 1 describes the measurement of efficacy and safety assessed during the study

Table (4.1.2) 1 - Investigation schedule

	Screening visit	Screening period – Inclusion	Induction phase							Withdrawal/ End-of-study			
			D3	D4	D5	D8	D10	D12	D17	D21	D24	D28	visit
Informed consent	X												
Screening criteria	X												
Height / Weight / BSA		X	X										
Inclusion / exclusion criteria		X											
Relevant medical / surgical history	X												
Previous treatments	X												i
Concomitant treatments	X		X	X	X	X	X	X	X	X	X	X	X
Pregnancy test (serum)		X											X
IRS randomization		X											
S95014 administration			X (see section 6.1)										
NIMP administration			(411 411 411 )	See Appe	rdix 1						l		
Pharmacokinetic assessment		l		вее пррег	uix 1								
Blood samples	I	I	X pre-dose, just after the infusion, 4h after the	X	X	X	X	X	X	X		X	
blood samples			end of infusion		48h after the end of infusion	Λ	Λ	Λ	Λ	Λ		Λ	
Pharmacodynamic assessment													
Plasma Asparaginase Activity							$X^2$		$X^2$	$X^2$		$X^2$	
Immunogenicity assessment													
Blood samples			X pre-dose						X			X	 
Safety assessments													
Vital signs		X	X pre-dose, post-infusion										X
Physical examination / ECOG		X	X pre-dose, post-infusion							 	 		X
ECG		X		X (see secti	ion 8.2)								X
Cardiac imaging 		X											X
Adverse events		X		X									X
Laboratory examinations													
Blood haematology		X	X				X		X		X		X
Blood biochemistry		X	X				X		Х		X		X
Blood coagulation		X	X				X		X		X		X
Urinary biochemistry		X	X				X		X		X		X
Hepatitis serology		X											X

<sup>2 Samples collected for PAA assessment will be the same as for PK assessment to avoid duplicating sample collection

For further practical details, methods of measurement are provided in sections 7, 8 and 9.

The maximum total volume of blood collected per participant during the study will be 200 mL. Additional blood samples will be collected in the frame of the ALL-MB 2015 protocol, as per local practice.

#### 4.2. Measures to minimise bias

This is a multicentre, randomized, open-label study. Subjects will be randomized to the liquid and lyophilized formulations according to a 1:1 ratio. The randomization will not be adaptive. No stratification factor will be used during randomization. The randomization will be centralized with an Interactive Response System (IRS).

During the study, pharmacokinetics, PAA and immunogenicity analysis will be performed in a specific central laboratory which will minimise the variability of measurements.

# 4.3. Study products and blinding systems

### 4.3.1. Products administered

S95014 liquid (reference drug) and S95014 lyophilizate (test drug) are both IMPs and will be manufactured under the responsibility of Les Laboratoires Servier Industrie (Gidy, France).

Currently, S95014 is not authorized in Russia in any of its formulations.

Table (4.3.1) 1 provides a description of the IMPs.

Table (4.3.1) 1 – Description of the IMPs (both S95014 formulations)

	S95014 Liquid	S95014 Lyophilizate
Pharmaceutical form Unit dosage	Solution for infusion 3750 U /5 ml vial	Powder for solution for infusion 3750 U /5 ml vial
Appearance, colour	Colourless solution	Lyophilized drug product: White to off white cake Reconstituted drug product: Colourless solution
	active ingredient per mL, monobasic sodium phosphate and dibasic sodium	

Table (4.3.1) 2 provides a description of the packaging of the IMPs.

#### Table (4.3.1) 2 – Description of S95014 packaging

Number of units of the pharmaceutical form per	- 3750 U S95014 /5 mL solution for infusion in an individual clear glass vial			
primary packaging	
 
4050 U of S95014 powder for solution for infusion in an individual clear glass vial
 
			
Number of primary packaging per secondary	· ·			
packaging	1 vial of S95014 lyophilizate per box			
Number of secondary packaging per patient and per	er The number of vials per patient will depend on the			
treatment period	patient's BSA			

The labelling of packages complies with the regulatory requirements of the country involved in the study.

Backbone therapy drugs will be administered as per ALL MB 2015 protocol (see Appendix 1). They will be regarded as NIMPs and will not be provided by the Sponsor. For further information about the NIMPs, please refer to section 6.1.2.

### 4.3.2. IMP management

S95014 liquid (reference drug) and S95014 lyophilizate (test drug) are both IMPs and will be manufactured under the responsibility of Les Laboratoires Servier Industrie (Gidy, France).

IMP receipt, dispensing according to the experimental design of the study (for the description of dispensing methods, refer to section 6.2), accountability and collection are the responsibility of the investigator and/or pharmacist of the medical institution.

IMP receipt and dispensing will be managed through an IRS.

Specific handling conditions and cleaning procedures will be described in the Pharmacy Manual.

# Stability and storage

The IMP should be stored in a secure area with restricted access. Specific storage conditions are mentioned on IMP labelling and are detailed in the Investigator's Brochure.

The investigator/pharmacist is responsible for the IMP temperature monitoring daily using FONT-CIRT-FORM-311 "Therapeutic Unit temperature log sheet - centre" (recording Min-Max temperature every working day) or an equivalent document.

In case of temperature deviation, the investigator/pharmacist should immediately:

- block the IRS for the concerned IMPs and place them in quarantine,
- alert the monitor or the local project manager if the monitor is absent, forward him all needed information and implement the instructions received.

Furthermore, the investigator/pharmacist must put in place an adequate corrective/preventive action once the first temperature deviation occurs in order to avoid recurrence.

IMP management will be verified on a regular basis by the study monitor.

The investigator and/or the pharmacist of the medical institution and/or a designated person from their study team must complete in real time all the documents provided by the sponsor concerning IMP management (therapeutic unit tracking form or an equivalent document...). Therapeutic unit tracking form, or an equivalent document, is the source document to fulfil.

The investigator and/or the pharmacist of the medical institution should only use the IMP provided for the participants involved in the study.

All defects or deterioration of IMPs or their packaging are to be reported to the study monitor, and to the IRS. The investigator will notify the monitor of all complaints set out by a participant (appearance...).

In the event of anticipated return of IMPs to the sponsor (batch recall), the sponsor will prepare an information letter intended for the investigator and/or pharmacist of the medical institution. This letter will be sent by the person locally responsible for the study to each study centre. On receipt of the letter, the investigator and/or the pharmacist will verify the presence of the IMP on site at the moment the incident becomes known, by using, among other tools, the therapeutic unit tracking form, or an equivalent document.

### Destruction

Destruction of the IMP is the responsibility of the sponsor and/or the investigator and/or the pharmacist of the medical institution.

Used remaining treatments will be locally destroyed and unused IMPs will subsequently be collected and stored according to the local procedures and requirements, by the person responsible for the IMP management.

A certificated destruction for unused IMPs will be performed according to standard modalities for that class of product and the attestation must be sent to the sponsor. The practical procedures for destruction of unused IMP will be defined by the sponsor and adapted to the centre. An IMP collection and destruction form will be completed before the shipment of IMP to destruction. Destruction of IMP may be possible when the product has been used, has expired or after at least the last visit of the last treated participant.

# 4.3.3. Management of blinding systems

Not applicable

### 4.4. Discontinuation of the study or temporary halt

### 4.4.1. Premature discontinuation of the study or temporary halt

This study may be temporarily halted or prematurely discontinued at any time for any sufficient reasonable cause.

After having informed the national coordinator, the sponsor or the Independent Ethics Committee (IEC) or the Competent Authority may terminate the study before its scheduled term. Two copies of the written confirmation will be dated and signed by the national coordinator. The IEC and Competent Authority will be informed according to local regulations.

If the study is prematurely discontinued, the on-going participants should be seen as soon as possible, and the same assessments as described in section 5.8 should be performed.

Under some circumstances, the investigator may be informed of additional procedures to be followed in order to ensure that adequate consideration is given to the protection of the participant's interests.

In case of study suspension (temporary halt), the study may resume once concerns about safety, protocol compliance, data quality are addressed and satisfy the Sponsor, the Independent Ethics Committee (IEC) and Competent Authority.

### 4.4.2. Premature discontinuation of the study in an investigator site (early site closure)

The sponsor reserves the right to close a study site at any time for any sufficient reasonable cause at the sole discretion of the sponsor.

The investigator may also initiate study-site closure at any time, provided there is reasonable cause and sufficient notice is given in advance of the intended termination.

Reasons for the early closure of a study site by the sponsor or investigator may include but are not limited to:

- Failure of the investigator to comply with the protocol, the requirements of the IEC or local Competent Authorities, the sponsor's procedures, or GCP guidelines
- inadequate recruitment of participants by the investigator
- Discontinuation of further study intervention development

The IEC(s) and Competent Authorities will be informed according to local regulations.

## 4.4.3. Discontinuation of the study in the event of objective reached

Not applicable

#### 4.5. Source data

Patient's medical file (e.g. ECG report, clinical laboratory examination's reports and all other patients' examination results), PK requisition forms will be considered as source documents.

Source data and source documents of the centre should be clearly identified in a specific, detailed and signed document before the beginning of the study.

### 5. SCREENING AND WITHDRAWAL OF PARTICIPANTS

### 5.1. Screening criteria

# 5.1.1. Demographic characteristics

1. Male or female patient aged  $\geq 1$  to  $\leq 18$  years

### 5.1.2. Medical and therapeutic criteria

- 2. Patients with cytologically confirmed and documented newly diagnosed ALL according to NCCN guidelines 2020 (see Appendix 2), excluding B-cell Burkitt ALL
- 3. Eastern Cooperative Oncology Group performance status (ECOG PS) 0-2
- 4. Women of childbearing potential (WOCBP) must use a highly effective method of birth control (both described in section 5.5) during study treatment and for 6 months after the last dose of IMP. In case of use of oral contraception women should have

been stable on the same contraceptive drug (i.e. same active principle) for at least 1 month prior to the first IMP administration. In case of use of hormonal contraception, WOCBP and male participants with WOCBP partners should use a second method of contraception, also called barrier method, such as male or female condoms, cap, diaphragm or sponge with spermicide. However, since there is a potential for an indirect interaction between S95014 and oral contraceptives, the concomitant use of S95014 and oral contraceptives is not recommended. A method other than oral contraceptives should be used in WOCBP.

5. Male participants with WOCBP partners must use a condom during the study and until at least 6 months after the last dose of IMP. In addition, contraception should be considered for their female partners. Contraceptive measures do not apply if the participant is sterile, vasectomized or sexually abstinent. Sperm donation will not be allowed during the study and for 6 months after the last dose of IMP.

#### 5.1.3. Informed consent

Obtained as described in section 13.3 of the protocol.

# 5.2. Non-screening criteria

### 5.2.1. General criteria

- 6. Unlikely to cooperate in the study
- 7. Pregnant and lactating women
- 8. Participation in another interventional study at the same time; participation in non-interventional registries or epidemiological studies is allowed
- 9. Participant already enrolled in the study (informed consent signed)

# 5.2.2. Medical and therapeutic criteria

- 10. Prior treatment with chemotherapy or radiotherapy (except steroids and intrathecal therapy)
- 11. Prior surgery or bone marrow transplant related to the studied disease
- 12. Down Syndrome
- 13. Psychiatric illness/social situation that would limit compliance with study requirements
- 14. Known carriers of HIV antibodies
- 15. History of previous or concurrent malignancy
- 16. History of sensitivity to polyethylene glycol (PEG) or PEG-based drugs
- 17. Pre-existing known coagulopathy (e.g. haemophilia and known protein S deficiency)
- 18. Known history of pancreatitis
- 19. Known history of significant liver disease
- 20. Significant laboratory abnormality likely to jeopardize the patients' safety or to interfere with the conduct of the study, in the investigator's opinion
- 21. Severe or uncontrolled active acute or chronic infection
- 22. Uncontrolled intercurrent illness including life-threatening acute tumor lysis syndrome (e.g. with renal failure), symptomatic congestive heart failure, cardiac arrhythmia

# 5.3. Inclusion criteria

Screening criteria must still be fulfilled at the time of the inclusion visit

#### 5.4. Non-inclusion criteria

Non-screening criteria must still be fulfilled at the time of the inclusion visit

#### **5.4.1.** General criteria

23. Women of childbearing potential tested positive in a serum pregnancy test within 7 days prior to the treatment period

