### 5.6. Retest management during screening period

A patient who has a laboratory result(s) that does not satisfy the entrance criteria may have the test (s) repeated once providing that the investigator judges it relevant according to the patient / participant previous results, or medical history and if s/he considers laboratory abnormalities are likely to be transient. Results of the test(s) repeated should be obtained within the allowed screening period. In this case the patient/participant will not be required to sign another informed consent, and the original patient / participant ID number assigned by the investigator will be used.

In any case, the last result available for each parameter must be considered for the patient/participant inclusion.

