# 6. TREATMENT OF PARTICIPANTS

### 6.1. IMPs and NIMPs administered

#### 6.1.1. IMPs

S95014 liquid (reference drug) and S95014 lyophilizate (test drug) are both IMPs.

Either lyophilized S95014 (arm 1) or liquid S95014 (arm 2) will be administered IV at the dose of 2500 U/m² at Day 3 of the induction phase, over 1-hour infusion. Please refer to latest version of the Investigator Brochure for further details.

S95014 dosage is calculated according to body surface area (BSA). The BSA will be calculated by the IRS based on the height and weight measured on the day of S95014 infusion (all BSA calculations are rounded to 2 decimal places). Height and weight measured within 4 days before the date of S95014 infusion will be acceptable.

BSA (m^2) =  $\sqrt{\text{Height [cm] x Weight [kg]/3600}}$ 

Study sites are required to use only calibrated and certified scales throughout the study.

If, for any reason, a patient included in the study is not able to receive S95014 at the prescribed dose of 2500 U/m² at the planned day, the infusion can be delayed. The day of S95014 administration will be regarded as Day 3 and the other treatments (backbone regimen used in the frame of ALL-MB 2015) will be postponed consequently. No dose reduction will be authorized during the induction phase. Beyond 14 days, if the patient cannot receive the IMP, he/she must be discontinued from the study.

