#### Laboratory tests

All laboratory tests performed during the study period will be assayed in an identified laboratory at hospital. Inter-visits laboratory tests could be assayed by local laboratories. In all cases, the full validated set of normal ranges values will be collected, as well as any update in these values during the study and must be documented in the corresponding eCRF pages.

All samples will be destroyed after mandatory assessment is completed and at the latest before the final version of the clinical report.

The laboratory parameters collection plan is described in Table (8.2) 1.

Blood haematology, blood biochemistry, blood coagulation and urinary analysis will be performed during screening, before S95014 infusion (Day 3, pre-dose), at Day 10, Day 17, Day 24 and during the withdrawal/end-of-study visit.

Other laboratory tests (i.e. hepatitis serology and pregnancy test) will be performed during screening and during the withdrawal/end-of-study visit.

**Test Category** Test Name Haematology Haematocrit, Haemoglobin, Red blood cells (RBC), White blood cells (WBC), Platelets, Differential (Basophils, Eosinophils, Lymphocytes, Monocytes, Neutrophils, Blasts in absolute value and in %) Albumin, Alkaline Phosphatase (ALP), ALT, AST, Ammonia, Bicarbonates, Gamma-Biochemistry glutamyl-transferase (GGT), Lactate dehydrogenase (LDH), Calcium, Phosphorus, Sodium, Potassium, Creatinine, Total Bilirubin, Total Cholesterol, LDL, HDL, Triglycerides, BUN or Urea, Uric Acid Amylase, Lipase, Glucose Urinary analysis Macroscopic Panel (Dipstick) (Blood, Glucose, Ketones, Protein) If the dipstick test is at least 2+ on one or more parameter(s), quantitative urinary biochemistry tests will be performed on the abnormal parameter(s) Prothrombin time - International Normalized Ratio (INR), fibrinogen, protein S activity, Blood coagulation antithrombin activity, activated Partial Thromboplastin Time (aPTT), D-dimer, FDP HbsAg, HbsAb, HbcAb, if HbsAg or HbcAb positive check viral load (HBV-DNA) at Hepatitis serology baseline, HCV RNA-PCR, HEV RNA-PCR Pregnancy Test Pregnancy testing is mandatory at inclusion (serum) and at withdrawal/end-of-study visit (serum) for WOCBP

Table (8.2) 1 - Local Clinical laboratory parameters collection plan

All samplings for biochemistry should be taken in fasting conditions.

Abnormal laboratory values or test/exams results (i.e. ECG recording) will constitute an AE if they are:

- associated with signs and symptoms, or

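### A delayed infusion triggers no repeat pregnancy test, so at the maximum 14-day delay the result can be 17 to 21 days old at dosing, against a 7-day window

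*Protocol*

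**What the plan says.** - **Window.** Criterion 23 (Protocol 5.4.1) excludes "Women of childbearing potential tested positive in a serum pregnancy test within 7 days prior to the treatment period".
- **Anchor.** Under Protocol 4.1.1 the "treatment period will start from the day of S95014 infusion, corresponding to Day 3 of the induction phase". The same section has the non-inclusion criteria checked at the Day 0 inclusion visit.
- **Scheduled tests.** In Table (8.2) 1, "Pregnancy testing is mandatory at inclusion (serum) and at withdrawal/end-of-study visit (serum) for WOCBP". The text of 8.2 is looser: "Other laboratory tests (i.e. hepatitis serology and pregnancy test) will be performed during screening and during the withdrawal/end-of-study visit". The pregnancy row of Table (4.1.2) 1 shows two marks; its layout is damaged in extraction, but two marks agree with 8.2.
- **Retests.** Section 5.6 allows one repeat of a laboratory result that fails the entry criteria, and "Results of the test(s) repeated should be obtained within the allowed screening period".
- **Delay.** Section 6.1.1 lets the infusion be postponed and treats the actual dosing day as Day 3. The limit is: "Beyond 14 days, if the patient cannot receive the IMP, he/she must be discontinued from the study".
- **A contrasting rule.** For dose calculation, 6.1.1 does tie a measurement to the actual date: "Height and weight measured within 4 days before the date of S95014 infusion will be acceptable".

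**The concern.** The 7-day window runs back from dosing, but the only pre-dose check is made at inclusion. When the infusion moves, the window moves with it and the test does not. Nothing in the schedule, the delay rule or the retest rule prompts a new one. Criterion 23 is also worded only as an exclusion for a positive result inside the window. It does not say that a negative result from inside the window must be on file before dosing, so having no in-window test breaches nothing explicitly.

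A site could therefore complete every scheduled step and still give a girl of childbearing potential her dose on a result outside the protocol's own window. The treatment is one 1-hour infusion. The instruction in 8.9.2.3 to stop the product if pregnancy occurs has no effect once the dose is in, so the pre-dose test is the checkpoint that matters. What is at stake is participant safety. The endpoints, analysis sets, power and type I error are not touched.

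**Working it through.** The plan states no figure for the age of the test at dosing, so there is none to reproduce. The check is day arithmetic.

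**Inputs**
- Planned infusion: Day 3 (4.1.1).
- Window: 7 days before the infusion (5.4.1 with 4.1.1).
- Criterion checked: Day 0 (4.1.1).
- Delay *d*: 0 to 14 days (6.1.1; 5.8.1 gives the same 14-day limit for delays due to adverse events). I count it from the planned Day 3.
- Test day *t*, on the original day count.

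**Formulas**
- Age at dosing = (3 − *t*) + *d*.
- In window if age ≤ 7, that is, if *d* ≤ 4 + *t*.

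**Which test days comply for an on-time infusion?** With *d* = 0, 3 − *t* ≤ 7 gives *t* ≥ −4. Since the check is made on Day 0, *t* ≤ 0. Compliant tests therefore fall on Day −4 to Day 0.

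| Test day | Age on time | Age at 14-day delay | In window for delays of | Out of window for delays of |
|---|---|---|---|---|
| Day 0 | 3 − 0 = 3 | 3 + 14 = 17 | 0 to 4 days | 5 to 14 days (10 of 14) |
| Day −4 | 3 + 4 = 7 | 7 + 14 = 21 | 0 days only | 1 to 14 days (14 of 14) |

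Excess over the window at maximum delay: 17 − 7 = 10 days to 21 − 7 = 14 days.

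The 8.2 text, read alone, would allow a test as early as Day −14. That would be 3 + 14 = 17 days old even on time, and 31 days old at maximum delay. It is left out of the range above because it misses criterion 23's window from the start.

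**Is there any later trigger for a test?**
- Table (4.1.2) 1 and 8.2: pregnancy tests at screening or inclusion and at end of study only. Section 8.2 does schedule haematology, biochemistry, coagulation and urinalysis before the infusion on Day 3, but not the pregnancy test.
- 5.6: applies to failed results within the screening period. A negative result that has merely aged is neither.
- 6.1.1: resets the day count and postpones the backbone treatment, with no re-check of eligibility.

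**How many participants?** The documents do not say. Assume that 10–20% of the 88 included are of childbearing potential and that 5–20% of infusions slip by more than 4 days:
- low: 88 × 0.10 × 0.05 = 0.44
- high: 88 × 0.20 × 0.20 = 3.52

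That is about 0.4 to 3.5 girls dosed on an out-of-window result. These are not pregnancies. The 4-day threshold fits a Day 0 test; earlier tests expire sooner, so for them the share of infusions that matters would be larger.

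**The case against.** The strongest reply is that the rule already follows the actual infusion. Criterion 23 counts back from the treatment period, that period starts at dosing, and 6.1.1 makes the real dosing day Day 3. A careful site could conclude that a 17-day-old result leaves it with no test inside the window, and repeat it. On this reading only a reminder is missing. The point about intent stands. It still supplies no mechanism: the criterion is checked at inclusion, excludes only a positive result, and is not revisited at dosing.

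Three further points have weight:
- **The range is a worst case.** It needs the full 14-day delay. The 21-day end also needs a Day −4 test. If testing at inclusion means strictly Day 0, only 17 days applies, and delays of up to 4 days do no harm. This stands, but 17 days is still 10 days outside the window.
- **Other safeguards exist.** Section 5.1.2 requires highly effective contraception, with a barrier method added to hormonal methods. Pregnancy is a non-screening criterion re-checked at inclusion and a reason for withdrawal. These make the residual risk small, but none of them detects a new pregnancy before a delayed dose.
- **Some documents are not available.** The SAP introduction cites a non-substantial protocol amendment of 7 April 2021. The SAP also places randomisation on Day 0, where Protocol 4.1.1 says Day 3, so that amendment may have revised the schedule. The content of Appendix 1 (ALL-MB 2015) is not available either, and whether it includes pregnancy testing cannot be known.

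The assumed rates behind the headcount have no source in the documents, so that range is illustrative only.

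**Conclusion.** The concern holds. In the protocol and SAP as available, no pregnancy test is scheduled or triggered when the infusion is delayed. A result that was in date for the planned infusion is 17 to 21 days old at the maximum delay, and is already out of date after a delay of 1 to 5 days, depending on when it was taken. This rests on counting the 14-day limit from the planned Day 3, and on neither the April 2021 amendment nor Appendix 1 already closing the gap. The number of girls concerned is small and the pregnancy risk low, so this is a worthwhile safety correction and not a threat to the trial's conclusions.

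**What to change.** First check whether the amendment of 7 April 2021 already deals with this. If it does not:

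1. State in 5.4.1 and 6.1.1 that participants of childbearing potential need a negative serum pregnancy test within 7 days before the actual infusion.
2. Add a conditional Day 3 pre-dose entry to Table (4.1.2) 1 and to 8.2: if the last result is more than 7 days old, repeat the serum test and see the result before dosing. Draw it with the pre-dose safety bloods already scheduled that day. The pre-dose PK sample, due within 15 minutes of the start of infusion, is likely to be too late for the result to come back.
3. Align the timing in the 8.2 text with Table (8.2) 1, so that both require the test at inclusion.

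With this change no participant of childbearing potential is dosed on a result more than 7 days old, whatever the delay. The cost is two sentences of protocol wording, one conditional table entry, an occasional repeat assay on blood already being drawn, and possibly a short wait before a delayed infusion.
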